1.8 Study Rationale

The most common side effect of glyburide is hypoglycemia. Sulfonylureas carry a rare but serious risk of increased cardiovascular mortality. Although the risk of cardiovascular mortality in patients receiving tolbutamide, a first-generation sulfonylurea, was 2.5 times that of patients treated with diet alone, subsequent studies have indicated that glyburide is not associated with an increased risk of cardiovascular events. A rare sulfonylurea-associated risk is hemolytic anemia in patients with G6PD deficiency and, in even more rare instances, in those without.

In contrast, dexamethasone causes disturbances in glucose metabolism in approximately 50% of patients, in addition to immunosuppression, femoral avascular necrosis, thrush, psychiatric disorders, and Cushing syndrome, among others.

In addition to a favorable side effect profile, the cost/benefit considerations of glyburide over alternatives merit consideration. The cost of a 30 day supply of glyburide is approximately \$30, compared with \$22 for dexamethasone. The cost of bevacizumab is approximately \$9,000/month.

Stereotactic radiosurgery (SRS) for brain metastases results in an approximately 5% incidence of radiation induced neurologic morbidity. Current interventional options include corticosteroids, pentoxifylline and vitamin E, surgery, hyperbaric oxygen, anticoagulation, and interstitial laser thermal therapy. More recently, bevacizumab has been shown to reduce T2/fluid-attenuated inversion recovery volumes on MR in patients with presumed SRS-induced radiation effects. A 90% improvement in neurologic symptomatology was noted; however, 61% of those patients experienced a return of neurologic symptomatology after discontinuation of anti-VEGF therapy. Because of the side-effect profile and high cost of anti-VEGF therapies, glyburide becomes an intriguing alternative as either prophylaxis against potential development of edema induced from radiotherapy or as a treatment alternative for existing edema that is at risk of becoming more significant with radiotherapy (1).

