3.0 PATIENT SELECTION

3.1 Conditions for Patient Eligibility

- 3.1.1** Patients with newly diagnosed brain metastases deemed to be eligible for radiosurgery.
 - 3.1.1.1** Prior whole brain RT and radiosurgery (to areas outside of the newly diagnosed brain metastases requiring radiosurgery) is allowed
- 3.1.2** Subject must have cytologically or histologically confirmed malignancy (this is the original malignancy, not the brain metastases).
- 3.1.3** A diagnostic contrast-enhanced MRI of the brain must be performed within 60 days prior to registration. The contrast-enhancing intraparenchymal brain tumor must be well visualized.
- 3.1.4** History and physical with neurological examination, height, and weight within 14 days prior to registration.
- 3.1.5** No dexamethasone use (or any other corticosteroid use with the purpose of treating cerebral edema) starting 5 days prior to SRS. Patients may be tapered to meet this criterion if deemed safe by the treating physician.
- 3.1.6** Women of child-bearing potential (e.g. not post-menopausal or permanently sterilized women) must have a negative pregnancy test obtained within 14 days prior to registration. This is to prevent potential harm to the fetus by glyburide and radiotherapy.
- 3.1.7** Age \geq 18 years of age.
- 3.1.8** Complete Blood Count (CBC) with differential and a Comprehensive Metabolic Panel (CMP) including Liver Function Tests (LFTs) obtained within 14 days prior to registration and meeting the following requirements:
 - Creatinine Clearance \geq 50 mL/min (by Cockcroft-Gault Equation).

- Total Bilirubin < 1.5 x the upper limit of normal (ULN).
- ALT and AST ≤ 2.5 x ULN.
- Glucose ≥ 80 mg/dL.
- Hemoglobin ≥ 7 mg/dL.
- Absolute Neutrophil Count > 100 cells/mm³.

3.1.9 For the Randomized Portion only:

3.1.9.1 Subject must have at least 2 of the following risk factors:

- Pretreatment Edema/Tumor ratio (≥ 35:1) as contoured on a baseline MRI obtained at most 60 days prior to registration. Patients are allowed to have Whole Brain Radiotherapy (WBRT) or corticosteroid use between the time of pretreatment MRI and SRS (as long as the corticosteroids can be safely tapered at least 5 days prior to the treatment planning MRI and WBRT is at least 4 days prior to registration).
- Greater than 40 pack year history of smoking cigarettes.
- Whole Brain Radiotherapy at least 4 days and no more than 1 year prior to registration.
- RPA Class III.

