3.2 Conditions for Patient Ineligibility

- 3.2.1** Known sulfonylurea treatment within 7 days prior to registration. Sulfonylureas include glyburide/glibenclamide (Diabeta, Glynase); glyburide plus metformin (Glucovance); glimepiride (Amaryl); repaglinide (Prandin); nateglinide (Starlix); glipizide (Glucotrol, GlibeneseR, MinodiabR); gliclazide (DiamicronR); tolbutamide (Orinase, Tolinsase); and glibornuride (Glutril).
- 3.2.2** Diffuse Leptomeningeal metastases.
- 3.2.3** Known allergy to sulfa or specific allergy to sulfonylurea drugs.
- 3.2.4** Use of VEGF inhibitors within 10 days prior to registration.
- 3.2.5** Allergy to gadolinium.
- 3.2.6** Type 1 diabetes mellitus or Type 2 diabetes mellitus actively receiving treatment.
- 3.2.7** Cognitive impairment that precludes a patient from acting as his or her own agent to provide informed consent.
- 3.2.8** Concurrent use of Bosentan.
- 3.2.9** Any major medical illnesses or psychiatric impairments that in the treating physician's opinion will prevent administration or completion of protocol therapy (which may include patients who are elderly, debilitated, or malnourished persons and/or those with renal, hepatic or adrenal insufficiency).
- 3.2.10** Pregnant or breast feeding women due potential damage to the fetus.
- 3.2.11** Inability to undergo MRI or SRS (e.g. due to safety reasons such as presence of a pacemaker).
- 3.2.12** Deemed by the treating physician to be unable to eat regular meals.

3.2.13 Patients currently on beta blockers.

3.2.14 Patient with a known diagnosis of ongoing alcoholism/alcohol abuse.

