4.1.3 Within 21 days prior to SRS

4.1.3.1 All patients will have a brain MRI with and without contrast suitable for SRS planning. T1-weighted, T2 and/or FLAIR MRI of the brain (maximum slice thickness 5mm). FLAIR imaging is preferred.

4.1.3.1.1 T1 post gadolinium sequence will be imported into the Eclipse treatment planning system and the radiation oncologist will contour the enhancing tumor that received the prescribed dose of SRS.

4.1.3.1.2 FLAIR sequence will be imported into the Eclipse treatment planning system. FLAIR volume will be automatically calculated using “Region Growing” on Eclipse (Appendix I). The automated contours will be verified and modified as needed by the radiation oncologist.

4.1.3.1.3 The MRI should be performed within 21 days prior to SRS treatment. A repeat treatment planning MRI is allowed. This MRI must meet the descriptions stated above in 4.1.3.1

4.1.4 5-9 days prior to SRS

4.1.4.1 Documentation of corticosteroid use/no dexamethasone (or any other corticosteroid with the purpose of treating cerebral edema) use.

4.1.4.2 Give patient a sufficient supply of non-micronized Glyburide tablets (1.25 mg) to be taken orally twice a day (in the morning with breakfast and in the evening with dinner). Missed doses will not be made up. Patient should be instructed to begin glyburide at least 5 days prior to SRS and continue glyburide until the evening dose of the one month post SRS MRI scan.

- 4.1.4.3** Provide patient with study supplies that include a medication/blood glucose log (for recording time of taking glyburide as well as time and value of blood glucose draws), a blood glucose monitor, and handouts for education purposes. The patient will be educated on how to measure and record blood glucose values (see Appendices II-VI).
- 4.1.4.4** Patient should begin fingerstick glucose draws 4 times a day beginning the day of glyburide initiation (in the morning before breakfast [fasting], before lunch, before dinner, and before bed). An additional fingerstick glucose draw will be taken by the nurse/research team member at this visit.

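### The protocol singles out G6PD deficiency as the main group at risk of hemolysis on a sulfonylurea, but no named eligibility criterion addresses it

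*Combined protocol and SAP*

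**What the plan says.** **The risk.** Section 1.8 lists the drug's side effects and states: "A rare sulfonylurea-associated risk is hemolytic anemia in patients with G6PD deficiency". It adds that people without the deficiency can also be affected, more rarely still. This is the only mention of G6PD in the supplied text.

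**Who may enter.** Section 3.1 asks for a blood count within 14 days before registration. Its only red-cell requirement is "Hemoglobin ≥ 7 mg/dL" (unit as printed). Section 3.2 has fourteen ineligibility items, and several deal with risks specific to this drug: drug-class allergy (3.2.3, "Known allergy to sulfa or specific allergy to sulfonylurea drugs"), bosentan (3.2.8), inability to eat regular meals (3.2.12), beta blockers (3.2.13) and alcohol abuse (3.2.14). The general item, 3.2.9, begins "Any major medical illnesses or psychiatric impairments" and applies where the treating physician thinks the condition "will prevent administration or completion of protocol therapy".

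**Exposure.** In the pilot (4.1.4) dosing starts no later than 5 days before SRS and ends on the evening of the one-month MRI. The dispensing visit is "5-9 days prior to SRS". The randomized portion uses the same timing for glyburide or placebo (4.2.4).

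**Follow-up and action.** Sections 4.1 and 4.2 and Appendix VIII schedule a blood count and an adverse event evaluation at 1 week, 1 month and 3 months after SRS. The DLT definitions are in 5.3 and are repeated in 7.3.4. The conditions for stopping study drug early are in 4.1.9 and 4.2.9.

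**The concern.** The protocol names a harm and the group most likely to suffer it, then lists its exclusions without mentioning that group. Comparable drug-specific risks were not left to general discretion; they have their own items in 3.2. The omission therefore looks like an oversight, since nothing in the text presents it as a decision.

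What is at stake is patient safety. Participants take glyburide for edema, not for glucose control, and patients on treatment for diabetes are excluded (3.2.6). A patient whose deficiency is already on record could be exposed to an avoidable risk that the protocol itself describes. Later safeguards are thin for this particular harm, which makes eligibility the main point at which the plan could act on it.

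**Working it through.** No figure in the plan needs reproducing. The check compares the sections with one another and does some visit-window arithmetic.

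**1. Does any criterion reach known G6PD deficiency?**
- 3.2.3 covers allergy. An enzyme deficiency is not an allergy.
- 3.2.9 depends on a major illness or psychiatric impairment and on the physician's opinion. Its examples (old age, debility, malnutrition, and renal, hepatic or adrenal insufficiency) are not exhaustive, but none is a red-cell condition. It allows a physician to exclude such a patient without requiring or prompting it.
- The hemoglobin floor in 3.1.8 measures current anemia. It does not identify the deficiency in someone who has not hemolyzed.
- No other item in 3.1 or 3.2 bears on the question.

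Result: not mandatorily excluded.

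**2. How long is the exposure?**
Days on drug = lead-in before SRS + days from SRS to the one-month MRI.
- Inputs: lead-in 5 to 9 days (4.1.4, 4.2.4); one-month visit at day 30, window -5 to +10, so day 25 to day 40 (Appendix VIII).
- Nominal: 5 + 30 = 35 days, or 5.0 weeks.
- Shortest: 5 + 25 = 30 days. Longest: 9 + 40 = 49 days.
- Counting both end days adds one. Sections 5.1 and 5.2 allow a lead-in of more than 5 days; the upper figure assumes that it stays within the 5-to-9-day visit.

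**3. When is the first on-study blood count?**
Days from first dose = lead-in + (7 ± 3).
- Earliest: 5 + 4 = 9 days. Latest: 9 + 10 = 19 days.
- Further counts follow at the one-month and three-month visits, so a fall in hemoglobin could be seen. Section 8.1.3 permits cytotoxic chemotherapy, which could make such a fall hard to attribute.

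**4. What would the protocol do about a hemolysis?**
- Concerning toxicity (5.3.1, 5.3.2): asymptomatic grade 3 or 4 hypoglycemia, or a non-hematologic grade 3 or higher event linked to low glucose and corrected by the glucose intervention.
- Serious toxicity: a death at least possibly attributable to the drug, or symptomatic grade 3 or 4 hypoglycemia with an unresolved non-hematologic grade 3 or higher event.
- Early stopping (4.1.9, 4.2.9): a DLT, or corticosteroids needed after registration and before SRS.

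A non-fatal hemolytic anemia by itself fits none of these. It would be recorded and reported under the general rules of 7.3 and would enter the pilot's secondary count of grade 2-5 toxicities (2.4.1.2). No DLT or early-stopping provision is tied to it. A fatal case attributed to the drug would be a serious toxicity.

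**The case against.** The best defense is that nothing here is a contradiction. Section 1.8 describes a rare class risk while arguing that the drug's side-effect profile is favorable; it does not say that deficient patients should be kept out. Accepting a rare risk without an exclusion is a legitimate judgement, and 3.2.9 lets a careful physician act. Blood counts are also done before registration and three times after SRS. Section 7.3.2 places the anticipated toxicities in the consent document, which is not among the supplied pages and may cover the risk.

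Much of this stands. The omission is an unexplained gap between two sections, and the importance of closing it is modest. What does not stand is that discretion closes it: 3.2.9 does not bring the condition to anyone's attention, and a consent statement would not change who is eligible.

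A reader might infer more than the documents support:
- *That a patient with known deficiency is bound to pass screening.* The Eligibility Checklist was not available, and 3.2.9 permits exclusion.
- *That G6PD deficiency is the whole of the risk.* Section 1.8 says that others can be affected, more rarely, so an exclusion would not remove the risk.
- *That one hemolysis would upset the pilot's safety decision.* A non-fatal case is not a DLT and does not count in the pilot rule (9.3.1).
- *That the gain is large.* With 30 evaluable patients planned on glyburide (10 + 20), the chance that at least one is deficient is 1 - (1 - p)^30, which runs from 14% at p = 0.5% to 96% at p = 10%. Those prevalences are assumptions, because the documents give none. The result concerns any deficiency, diagnosed or not. It measures neither known cases, which are all that a history item would catch, nor hemolysis, which the protocol calls rare.

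**Conclusion.** The point holds in a limited form. Section 1.8 identifies G6PD deficiency as the main, though not the only, group at risk, and no named criterion in 3.1 or 3.2 addresses it. A patient with known deficiency may be enrolled unless a physician chooses to use 3.2.9. That patient could then receive nominally 35 days of glyburide (30 to 49 across the windows): with certainty in the pilot, and in the randomized portion only if allocated to glyburide.

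The first on-study count comes 9 to 19 days after the first dose, assuming a lead-in of 5 to 9 days. The DLT and early-stopping rules do not cover a non-fatal hemolysis.

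The size is small. The benefit is patient protection only, confined to patients whose deficiency is already known and to an event described as rare. The documents do not allow the number of patients affected to be estimated. The endpoints, power and pilot decision rule are unaffected. The case for acting is that the protocol acknowledges the harm and the remedy costs almost nothing.

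**What to change.** Reconcile 3.2 with 1.8 for both portions. One way is to add an item on known G6PD deficiency to 3.2, based on history alone like the allergy and alcohol items, with a matching line in the Eligibility Checklist. If the sponsor means to accept such patients, 3.2 or 1.8 should say so and give the reason. The clinical rule is the sponsor's decision.

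The cost is one line in an amendment and one checklist entry. No new laboratory test is needed, and dose, schedule, sample size and analysis stay as they are. The downside of an exclusion is the loss of the rare patient with known deficiency.

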Developing a mechanism to predict which patients are at highest risk of developing edema after SRS is important when designing a potential randomized trial in order to select patients who may benefit most from prophylactic oral glyburide administration. A retrospective analysis at the University of Maryland Medical Center, Department of Radiation Oncology examined 55 patients treated with SRS using the Gamma Knife for brain metastases and analyzed potential predictors for volumetric increase in edema from MR imaging obtained no more than 30 days before SRS, compared with post-treatment MR imaging obtained no later than 100 days after SRS. Multivariate analysis of preliminary data suggests that melanoma/renal primary histology, Recursive Partitioning Analysis class III, large pre-treatment edema-to-tumor ratio, and prior whole brain therapy all increase the risk of volumetric edema increase after SRS. Patients with melanoma/renal primaries had a lower pre-treatment edema volume than other primaries but had the largest increase in edema

after SRS when compared to those with other histologies (Figure 2). Patients that possessed 2 or more of these risk factors had a 35% chance of volumetric edema increase as measured on axial T2 imaging as compared to an 8% risk of edema increase in patients with less than 2 risk factors. Edema increase was measured from time of MRI obtained no earlier 30 days prior to SRS compared to MRI obtained no later than 100 days after SRS. Absolute edema was calculated by subtracting the contoured tumor volume from the contoured edema volume. Absolute edema that was < 1.00 cc was not considered edema. Edema increase was defined as an absolute increase in 5% from the time of pre SRS MRI to the time of post SRS MRI.

Variable	Edema increase	No edema increase	% with increased edema	P value*
Primary histology				
Melanoma or RCC	9	15	38%	
Others	14	76	16%	
RPA class				
I or II	11	72	13%	
III	10	21	32%	
Metastasis location				
Infratentorial	1	23	4%	
Supratentorial	20	70	22%	
Prior WBRT				
Yes	17	53	24%	
No	4	40	9%	
Figure 2: Data from Hanna et al. demonstrates odds of developing increased cerebral edema associated with certain risk factors (15).				
RCC: Renal Cell Carcinoma / WBRT: whole brain radiation therapy				

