T1 post-gadolinium sequences and FLAIR axial sequences from the treatment planning MRI (see note above regarding linac-based radiosurgery patients) and at the one and three month follow-up appointments will be imported into the Eclipse treatment planning system. On the T1 post gadolinium sequences, the radiation oncologist will contour the enhancing tumor that received the prescribed dose of SRS. Using the FLAIR sequences Eclipse will automatically calculate FLAIR volume using “Region Growing” (Appendix I). The automated contours will be verified and modified as needed by the radiation oncologist. Physicians, patients, and the study team will be blinded to the patient’s investigational medication.

5.2.1 Patients can only be enrolled after all eligibility criteria are met. The date of registration/enrollment/study entry is considered to be the day the Eligibility Checklist is signed by the verifying physician and should be no later than 5-9 days prior to SRS. Once a patient is enrolled, a unique case number will be assigned to the patient and blinded randomization will occur. Patients will be randomized by the UAB Investigational Drug Services (IDS) Pharmacy, who will hold the blind for this study.

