9.3 Analytic plan for primary objective

9.3.1 Pilot Portion: Each evaluable patient will be assessed for “*concerning toxicities*” and “*serious toxicities*”. If 6 or more patients demonstrate a “*concerning toxicity*” or 1 or more patients experience a “*serious toxicity*”, the therapy will be considered not feasible to deliver and one dose reduction will occur. If 6 or more patients demonstrate a “*concerning toxicity*” or 1 or more patients experience a “*serious toxicity*” on the dose reduced schedule, the intervention will be considered too toxic and the protocol will be terminated. Inevaluable patients will be replaced.

9.3.2 Randomized Portion:

After the acceptable glyburide dose has been established, the randomized portion will commence. No formal interim monitoring will take place and study analysis will be done when all 20 randomized patients are accrued in each treatment regimen. The results from this portion of the trial will be used as a screening mechanism for assessing whether glyburide should be studied in a formal randomized trial. The number of patients who experience treatment successes will be compared between the two regimens using the

exact test of proportions. If this test yields a one-sided test of equality of proportions of treatment success obtains a p-value of 0.30 or less, glyburide treatment will be considered as sufficiently interesting for further study. Otherwise, glyburide will be considered not interesting for further development. We acknowledge that the type 1 error rate of 0.30 is liberal, and note that this was chosen based on the preliminary efficacy aspect of the study; post-analysis power calculations may be performed.

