9.5 Sample size justification

9.5.1 Pilot Portion

- 9.5.1.1** *For serious toxicities:* If the true rate of a “*serious toxicity*” with oral glyburide is 30%, the treatment will be considered not tolerable with probability 97%. If the regimen has a true rate of grade 3 hypoglycemia of 1%, the therapy will be considered tolerable with probability 90%.
- 9.5.1.2** *For concerning toxicities:* If the true rate of a “*concerning toxicity*” with oral glyburide is 30%, the treatment will be considered tolerable with probability 95%. If the regimen has a true rate of “*concerning toxicity*” of 70%, the therapy will be considered not tolerable with probability 85%.
- 9.5.1.3** The purpose of the pilot portion is to ensure feasibility of enrollment and safety of administering glyburide in patients with brain metastases that receive radiosurgery. These first 10 patients will undergo more extensive blood sugar evaluation than what is planned in the randomized portion. Once glyburide has been deemed safe and timely enrollment feasible, only then will we proceed to the randomized portion. The randomized portion will still assess hypoglycemia, but will utilize more standard hypoglycemia testing procedures. Our statistical group deemed 10 patients to be an appropriate number to ensure that rates of concerning hypoglycemia were not too high.

- 9.5.2** Randomized Portion: We expect the treatment success rate for the placebo will be 50% based on historical experience (15). The historical data from Hanna et al. was retrospectively evaluated from patients who received radiosurgery at University of Maryland. Many patients received dexamethasone during the course of radiosurgery and immediately thereafter, which likely resulted in a lower number of patients who experienced a clinical or radiographic increase in edema than if steroids were not utilized. The rationale for adding in a placebo group is to allow for a purer evaluation of the control

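### The randomized go/no-go comparison neither stratifies nor adjusts for prior WBRT, a predictor the protocol itself names; doing both would make the decision more robust at almost no cost

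*Combined protocol and SAP*

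**What the plan says.** Section 1.8 reports a multivariate analysis of a retrospective series, in which melanoma or renal histology, RPA class III, a large edema-to-tumor ratio and "prior whole brain therapy all increase the risk of volumetric edema increase after SRS". Figure 2 gives the counts by factor.

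Section 3.1.9.1 requires at least two of four risk factors for the randomized portion. One of them is "Whole Brain Radiotherapy at least 4 days and no more than 1 year prior to registration", so WBRT status can be fixed before randomization without new data.

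On allocation, section 5.2.1 says "Patients will be randomized by the UAB Investigational Drug Services (IDS) Pharmacy". It mentions no strata and no blocks.

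On analysis, section 9.3.2 says "The number of patients who experience treatment successes will be compared between the two regimens", by an "exact test of proportions", and "study analysis will be done when all 20 randomized patients are accrued in each treatment regimen". Glyburide goes forward on this condition: "If this test yields a one-sided test of equality of proportions of treatment success obtains a p-value of 0.30 or less". No adjusted, stratified or sensitivity analysis of the primary outcome is described there or in section 9.4.

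**The concern.** The trial ends in one yes/no decision from 40 patients, with no formal interim look. At that size a binary baseline factor can easily differ between arms by several patients. If the factor predicts failure, a crude comparison then partly reflects the imbalance. Fewer WBRT patients on glyburide makes a false go more likely. More of them on glyburide makes it more likely that a useful drug is dropped. Section 9.5.2 says the result decides whether the idea moves to a cooperative group, so both errors matter. The plan names the predictor and already uses it at entry, but brings it into neither the randomization nor the test.

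**Working it through.** **Inputs from the plan.** 20 per arm and one-sided p ≤ 0.30 (9.3.2). Placebo success 50% ("We expect the treatment success rate for the placebo will be 50% based on historical experience"), glyburide success 75% and power 0.80 (9.5.2). Figure 2, prior WBRT: 17 of 70 with edema increase, against 4 of 44 without prior WBRT.

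**Assumptions that are not in the plan.** 60% of randomized patients have had WBRT, and the WBRT odds ratio for treatment failure is varied from 1 to 3.2.

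**Step 1: the plan's own figure.** I enumerated two binomials of size 20 with the one-sided Fisher test. With success 0.75 against 0.50, P(p ≤ 0.30) = 0.802, which reproduces the stated 0.80. With 0.50 in both arms it is 0.215, below the nominal 0.30. In practice a go needs about three more successes on glyburide: 13 against 10 gives p = 0.26, and 12 against 10 gives p = 0.38.

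**Step 2: the crude odds ratio.** (17 × 40) / (53 × 4) = 680 / 212 = 3.2.

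**Step 3: failure rates by WBRT.** Solve 0.6 × f(yes) + 0.4 × f(no) = 0.50 for placebo, and 0.25 for glyburide, at the given odds ratio. At 3.2 this gives 0.613 and 0.331 on placebo, and 0.328 and 0.133 on glyburide. Check: 0.6 × 0.613 + 0.4 × 0.331 = 0.50. Under no drug effect, a 5-patient imbalance shifts the expected difference in successes by 5 × (0.613 − 0.331) = 1.4, about half the margin of three.

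**Step 4: the crude test with WBRT counts held fixed** (glyburide / placebo). Each cell is false-go / power.

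| WBRT counts | OR 3.2 | OR 2 | OR 1.6 |
|---|---|---|---|
| 12 / 12 | 0.205 / 0.810 | 0.211 / 0.805 | 0.213 / 0.803 |
| 10 / 14 | 0.327 / 0.888 | 0.281 / 0.856 | 0.259 / 0.840 |
| 14 / 10 | 0.116 / 0.706 | 0.153 / 0.744 | 0.172 / 0.763 |
| 9 / 14 | 0.361 / 0.902 | 0.300 / 0.867 | 0.272 / 0.847 |
| 14 / 9 | 0.099 / 0.672 | 0.141 / 0.725 | 0.163 / 0.750 |

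At an odds ratio of 1.25 a 5-patient imbalance gives false-go of only 0.19 to 0.24.

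**Step 5: how often.** With the two arms as independent draws at 60% WBRT, a difference of 4 or more in either direction has probability 0.26, and in glyburide's favour 0.13. A difference of 5 or more in glyburide's favour has probability about 0.07. If exactly 24 of the 40 have had WBRT, a difference of 4 or more in either direction has probability 0.33.

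**Step 6: the exact test stratified by WBRT.** At an odds ratio of 3.2, false-go is 0.196 to 0.205 and power 0.787 to 0.810 in all five rows. With balanced strata (12 / 12), false-go is 0.205 to 0.215 and power 0.80 to 0.81 for every odds ratio from 1 to 3.2. If randomization is not stratified, the stratified test costs about 1 point of power on average (for example, 0.802 to 0.791 at an odds ratio of 1). At an imbalance it costs up to 2.5 points (0.802 to 0.777).

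**The case against.** The strongest reply is that nothing in the plan's error rates is wrong. Randomization already allows for chance imbalance, the crude exact test is a standard choice at this size, and section 9.3.2 describes the trial as a screen with a deliberately liberal threshold. This stands. A reader might infer from 0.10 to 0.36 that the type I error is inflated. The documents do not support that: these values are conditional on one particular imbalance, and their average over randomizations is 0.215.

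The second reply is that an odds ratio of 3.2 does not carry over to this trial. Most of this also stands:

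- Every randomized patient has at least two risk factors, so a patient without WBRT has two others. In an illustrative model with four independent factors, an odds ratio of 3.1 each and assumed prevalences of 0.2 to 0.6, the marginal odds ratio of one factor falls to about 1.25 to 1.6.
- Figure 2 concerns volumetric increase on MRI up to 100 days after SRS. The success or failure tested in 9.3.2 is defined in 9.1.2 by corticosteroid initiation, or related death, by the one-month MRI.
- The rows of Figure 2 total 114 against 55 patients, so the unit appears to be the lesion. Even treating the lesions as independent, the 95% interval for the WBRT odds ratio is about 1.0 to 10.3.
- Figure 2 covers any prior WBRT; the entry criterion is WBRT within 1 year.
- With the WBRT rates as printed (24% and 9%), and about half of patients with WBRT, a 5-patient imbalance gives false-go of only 0.08 to 0.23. The value 0.36 needs the overall failure rate rescaled to 50%.

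The third reply is that WBRT is one of several predictors, and stratifying on it leaves the others to chance. That is also true. These replies reduce the size of the point. They do not give a reason to leave the factor unused, because the paired change costs essentially nothing even if WBRT proves to have no effect.

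**Conclusion.** The point holds as a modest robustness improvement. The plan's stated power is right, and its false-go rate is below the nominal 0.30. What is missing is protection of the single realized trial against chance imbalance in a factor the protocol itself calls predictive.

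Assuming 60% WBRT and 50% failure, a 5-patient imbalance moves false-go over 0.10 to 0.36 at an odds ratio of 3.2, 0.14 to 0.30 at 2, and 0.16 to 0.27 at 1.6. Power moves over 0.67 to 0.90, 0.73 to 0.87 and 0.75 to 0.85 respectively. A 4-patient imbalance at 3.2 gives false-go of 0.12 to 0.33, so the widest range should not be attached to it. The lower odds ratios are the more plausible ones here. The documents cannot settle the value.

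**What to change.** Make two changes together.

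- Section 5.2.1: the IDS pharmacy uses a 1:1 blocked list stratified by WBRT within 1 year before registration (yes/no).
- Section 9.3.2: the primary test is the one-sided exact test stratified by that factor (exact Cochran-Mantel-Haenszel), with the 0.30 threshold unchanged. The crude exact test is reported beside it.

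They belong together because, without stratified randomization, the stratified test gives up the small amount of power shown in the working.

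The cost is a two-stratum list and a sentence in each section, with no added patients, visits or data. The limits are that one factor must be fixed in advance, and that imbalance in RPA class, edema-to-tumor ratio, smoking history or histology is not addressed.
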